13. SAFETY AND TOLERABILITY ANALYSIS

Safety analyses will use the SAS population.

13.1 Safety and tolerability endpoints

Safety and tolerability will be assessed by using the following endpoints:

1. The incidence, type and severity of AEs
2. Changes from baseline in clinical laboratory parameters
3. Changes from baseline in vital signs
4. Clinically meaningful changes from baseline in physical examination
5. Clinically meaningful changes from baseline in electrocardiogram (ECG)
6. Tolerability: Local tolerability in terms of skin reaction at 0.5h and 2h after post-dosing (note that local tolerability events are reported as adverse events as well)

13.2 Baseline values

For assessments with post-dose measurements (e.g. ECG, vital signs, safety laboratory) the pre-dose value at the respective dosing visit will be taken as baseline value.

14. METHODS OF SAFETY ENDPOINT ANALYSIS

Tabulations will show results for the SAS population.

14.1 Adverse events

14.1.1 Definitions

For specific regulations of documentation of adverse events (AEs), please refer to the study protocol.

Documentation: Adverse events are recorded under the eCRF section adverse events. Clinical events of interest (hemodynamic changes) are recorded in this section as well. For a definition of clinical events of interest refer to sec. Definitions. AEs being an clinical event of interest can be depicted by using eCRF field 'Is this a clinical event of interest?'. Furtheron signs and symptoms associated with the clinical event of interest are documented and coded. Blood pressure and pulse rate belonging to the sign is recorded. AEs referring to local tolerability can be depicted using the eCRF field 'Injection site reaction?'.

Coding: All AEs reported in this study will be coded using MedDRA, current version 20.0 or higher.

Causal relationship: Causal relationship between the occurrence of an AE and the administration of the study drug is assessed by the investigator according to classification scheme 0=not related, 1=unlikely related, 2=possibly related and 3=probably related. Probable and possible relationship are subsumed under the category related. All AEs must have a causal relationship assigned. In case of a missing relationship, a query will be raised in order to obtain causality assessment. In case no clarification of relationship via query is possible the missing relationship will be set to related for the analysis.

Severity/ Intensity: Severity/ intensity grading will differ between 1=mild, 2=moderate and 3=severe. For AEs having a missing severity, the severity will not be imputed and kept as missing.

Tabulation: All AE tabulations will be presented by treatment group.

Listings: An additional flagging will show adverse events accounted to the screening and to the interventional study phase. Duration of adverse events: the duration of the adverse events will be presented using start and end date of the adverse event.

Adverse events accounted to screening and to the interventional phase: For the assignment of AEs to the screening or the interventional phase, the following algorithm will be applied:

- If the onset date of the AE is at the same day or after the start of the IMP drug administration date, then the AE is classified to the treatment period and is therefore treatment-emergent. For the adverse events accounting to the screening phase the start date of the adverse event may not be later than the start date of the interventional phase (= date of first administration of the IMP).
- If any date part is missing, the procedures for imputing missing date parts should be applied first.

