7.4.2 Treatments administered

Dasiglucagon is a stable peptide analog of human glucagon in a ready-to-use liquid formulation indicated for treatment of severe hypoglycemia in insulin dependent patients with diabetes mellitus. Dasiglucagon is in clinical development and has no marketing authorization as yet. GlucaGen is approved in the EU and US and is indicated for treatment of severe hypoglycemic reactions, which may occur in the management of insulin-treated children and adults with diabetes mellitus.

Patients in this trial have not previously been treated with dasiglucagon (ZP4207) and will be randomly assigned (1:1) to receive 1 of the following trial medications:

- 0.6 mg dasiglucagon
- 1 mg GlucaGen

Prior to administration of trial medication at all dosing visits patients must reach a target plasma glucose level of 70-150 mg/dL. If the patient presents with plasma glucose > 150 mg/dL, corrective amounts of fast acting insulin will be administered at the investigator's discretion. Plasma glucose measured after 20 and after 40 minutes should ensure that the patient has reached the targeted 70-150 mg/dL. If the patient presents with plasma glucose < 70 mg/dL glucose ingestion will be provided in order to reach target plasma glucose of 70-150 mg/dL documented by plasma glucose measurements after 20 and 40 minutes, respectively.

Following the first (Visit 2) and third (Visit 4) dose administration, patients must be fasting for 90 min after dosing. Following the 90-min blood sample draw after the administration of the first (Visit 2) and third (Visit 4) dose administration, patients may be treated individually in order to alleviate any potential side effects in order to minimize premature treatment discontinuation and consequently reduce the amount of missing data. This treatment can also be instituted immediately after the second dose administration (Visit 3), as pharmacodynamics will not be assessed at this visit.

In order to minimize the number of patients discontinuing treatment prematurely and consequently reduce the amount of missing data, the following treatment modalities may be used, as considered appropriate by the investigator:

At visit 2 and 4:

- 90 min after dosing patients will be allowed to eat and drink moderately to make them feel comfortable
- 90 min after dosing a moderate and individualized corrective dose of insulin to convert the induced hyperglycemia to euglycemia, after agreement with the investigator

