8.2 Collection, recording and reporting of adverse events

All events meeting the definition of an AE must be collected and reported from the first trial related activity after the patient has signed the informed consent until the end of the post-treatment follow-up period. At each contact with the site (visit or telephone, excluding visits, where the patient is not seeing the Investigator or his staff (e.g. visits to the laboratory)) the patient must be asked about AEs. All AEs, either observed by the Investigator or reported by the patient, must be recorded by the Investigator and evaluated.

The Investigator should record the diagnosis, if possible. If no diagnosis can be made the Investigator should record each sign and symptom as individual AEs.

All AEs must be recorded by the Investigator. One single Adverse Event Form must be used per AE from start to resolution. For SAEs, the Serious Adverse Event Form must also be completed. For clinical events of interest, the Clinical Event of Interest Form must also be completed.

AE information should include the following:

- Date and time of onset and resolution
- Date and time of Investigator's first information on the (S)AE
- Seriousness
- Severity
- Causal relationship with IMP
- Interruption or withdrawal of treatment with IMP and other measures taken
- Outcome

All AEs are coded; details are described in the trial specific Data Management Plan.

If an event classifies as a clinical event of interest, the Investigator must tick the Clinical Event of Interest box on the AE form and complete the Clinical Event of Interest Form. The Clinical Event of Interest form will capture if the event was associated with any signs or symptoms and capture the highest/lowest blood pressure and pulse measured during the event.

The Investigator must report initial information in writing (fax or email) on all SAEs to the Sponsor's responsible pharmacovigilance unit (Safety CRO) immediately (within 24 hours) after

obtaining knowledge about the event. Please refer to Appendix 1 for contact details. The Safety CRO will inform the medical monitor and the sponsor about the reported SAEs.

It is the responsibility of the Safety CRO to report all SUSARs that occur in this trial to the Competent Authorities and IRBs/IECs in accordance with the local requirements in force and ICH guideline for GCP. The trial monitor must be informed accordingly.

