8.4 Hypoglycemia

Hypoglycemia will be regarded as an AE and recorded and documented on an AE Form.

Hypoglycemia is defined as a fall of plasma glucose below 3.9 mmol/L (70 mg/dL).

During the dosing visits, mild to moderate symptoms of hypoglycemia, or a blood glucose (BG) value less than a threshold of <2.8 mmol/L (50 mg/dL), corresponding to a plasma glucose (PG) value of <3.1 mmol/L (56 mg/dL), will be treated by i.v. glucose solution at the investigator's discretion according to best available medical practice. Treatment is to be repeated until BG value stabilized above the threshold limit again. BG measurements will only be done due to safety concerns. Insulin-induced hypoglycemia should be recorded as an AE.

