APPENDIX C: LIST OF TABLES, FIGURES, AND LISTINGS	51
LIST OF TABLES AND FIGURES FOR ANALYSIS	51
LIST OF DATA LISTINGS FOR ANALYSIS	57
APPENDIX D: TABLE LAYOUTS	59

LIST OF ABBREVIATIONS

ADA	Anti-drug antibody
AE	Adverse event
ATC	Anatomical therapeutic chemical
AUC _{0-30min}	Area under the plasma concentration curve from administration to observed concentration 30 min
AUC _{0-90 min}	Area under the plasma concentration curve from administration to observed concentration at 90 min
AUE _{0-30min}	Area under the effect curve from administration to 30 min
AUE _{0-90 min}	Area under the effect curve from administration to 90 min
CE _{max}	Change from baseline plasma glucose to maximum plasma glucose measured post dose
CFB	Change from baseline
CI	Confidence Interval
C _{max}	Maximum plasma concentration
CRF/eCRF	Case report form/electronic case report form
CSR	Clinical study report
e.g.	For example
ECG	Electrocardiogram
EoT	End of Trial
FAS	Full Analysis Set
ICH	International conference on harmonization
IMP	Investigational Medicinal Product
MedDRA	Medical Dictionary for regulatory activities
NAb	Neutralizing Antibody
PD	Pharmacodynamic(s)
PK	Pharmacokinetic(s)
PPS	Per protocol set
PT	Preferred term
SA (set)	Safety analysis (set)
SAE	Serious adverse event
SAP	Statistical analysis plan
SAS	Safety analysis set
SD	Standard deviation
SHCR	Contract research organization: SynteractHCR Deutschland GmbH, [name], 80636 Munich, Germany
SOC	System organ class

T1DM	Type 1 diabetes mellitus
T2DM	Type 2 diabetes mellitus
TEAE	Treatment-emergent adverse event
TLFs	Tables, listings, figures
t_{\max}	Time until C_{\max} is reached, time to maximum effect
ULN	Upper Limit of Normal
V	Visit
WHO	World Health Organization
WHO-DDE	WHO drug dictionary enhanced
ZP4207	dasiglucagon

DEFINITIONS

Treatment-emergent AE	AEs with an onset time at or after the initial dose of study drug.
End of trial	The trial ends with the last visit of the last patient participating in the trial.

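### SAP 14.1.1 flags treatment-emergent AEs by calendar date while the SAP's own definition uses onset time, so AEs before the first injection on Day 0 are counted as treatment-emergent and also meet the screening condition

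*SAP*

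**What the plan says.** Three pieces of current SAP text bear on the flag.

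- The definitions at the front of the SAP describe treatment-emergent AEs as "AEs with an onset time at or after the initial dose of study drug".
- SAP 14.1.1, which gives the algorithm to be applied, tests the calendar date: "If the onset date of the AE is at the same day or after the start of the IMP drug administration date". Any event passing this test is assigned to treatment and flagged as a TEAE.
- The same bullet then says of screening AEs that "the start date of the adverse event may not be later than the start date of the interventional phase", which it equates with the date of first IMP administration.

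Neither 14.1.1 nor the imputation rules in SAP section 9 contains a time-of-day condition. Section 9 deals only with missing parts of dates.

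In protocol version 3, section 8.2 requires that AEs "must be collected and reported from the first trial related activity after the patient has signed the informed consent", so the pre-dose hours of Day 0 fall within collection. The same section lists "Date and time of onset and resolution" among the AE information. Section 7.5.2 allows a small breakfast with rapid-acting insulin on dosing days. Section 7.4.2 provides that, if plasma glucose exceeds 150 mg/dL before dosing, "corrective amounts of fast acting insulin will be administered at the investigator's discretion", and that glucose is given if the patient presents below 70 mg/dL. Section 8.4 defines hypoglycemia as plasma glucose below 70 mg/dL and adds: "Insulin-induced hypoglycemia should be recorded as an AE".

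**The concern.** Two rules in one SAP give different answers for the same event, and the one that will be programmed departs from the stated definition. They differ only on the calendar day of the first injection, before that injection. In this trial that period is not empty: glucose is actively adjusted then, and low values are recordable AEs.

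The secondary objective is to evaluate safety and tolerability compared with GlucaGen. Events that the trial drug cannot have caused would enter the TEAE overview (SAP 14.1.2) and the tables by system organ class, preferred term, causality and intensity (SAP 14.1.3). The overview also has a separate row for AEs during screening. Because the two date conditions overlap on Day 0, two programmers could fill the screening and TEAE rows differently and each could point to the text.

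**Working it through.** The plan gives no figure to reproduce. The check applies each rule to test onsets and then illustrates the possible size.

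**Rules.** Let the first injection be at 10:00 on Day 0. The definition requires onset date-time ≥ injection date-time. The algorithm requires onset date ≥ injection date. The screening sentence requires onset date ≤ injection date.

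| Onset | TEAE by definition | TEAE by algorithm | Meets screening sentence |
|---|---|---|---|
| Day -1, 20:00 | no | no | yes |
| Day 0, 09:20 | no | **yes** | **yes** |
| Day 0, 10:30 | yes | yes | **yes** |
| Day 7, 09:20 | yes | yes | no |

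The definition and the algorithm disagree in one row only, Day 0 before the injection. The screening sentence overlaps with the algorithm for every Day 0 event, including those after the injection. Pre-dose events on Day 7 are treatment-emergent under both rules, and the same holds for Day 14, because they follow the first dose.

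**Illustration of size.** Inputs:

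- 112 patients planned (SAP sections 4 and 5), randomized 1:1, so 112 / 2 = 56 per arm.
- q, the share of patients with an AE before the first injection on Day 0. This is an assumption, ranged from 2% to 20%; the documents give no value.
- p, the share with a true TEAE. This is an assumption, taken as 10% and 50%.
- Independence of the two, also assumed.

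Extra patients per arm in a hypoglycemia preferred-term row, if none of them also has hypoglycemia later, are 56 × q:

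- q = 2%: 56 × 0.02 = 1.1
- q = 20%: 56 × 0.20 = 11.2

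In the any-TEAE row the observed proportion is 1 − (1 − p)(1 − q), so extra patients are 56 × q × (1 − p):

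- p = 10%: 56 × 0.02 × 0.9 = 1.0, up to 56 × 0.20 × 0.9 = 10.1
- p = 50%: 56 × 0.02 × 0.5 = 0.6, up to 56 × 0.20 × 0.5 = 5.6

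**Effect on the comparison.** With the same q in both arms, the observed difference in patient incidence is (1 − q) × (p₁ − p₂), so it shrinks by 2% to 20% over this range. Check at q = 10%: p = 50% becomes 0.55 and p = 10% becomes 0.19; the difference is 0.36 = 0.9 × 0.40. Differences in event counts are unchanged on average. Ratios move towards one.

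**The case against.** A reader might infer that the rule attributes low-glucose events to drugs that raise glucose. The documents do not support that. Treatment-emergent is a statement about timing. Causality is assessed separately by the investigator, and SAP 14.1.3 tabulates drug-related TEAEs on their own. A pre-dose event would enter those tables only if the investigator judged it related, or if causality were missing and a query failed, in which case SAP 14.1.1 sets it to related.

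A reader might also infer a bias towards one arm, or a large error. Neither follows. Events before the first injection cannot depend on the assigned drug, so they are balanced in expectation. The date rule over-includes and cannot drop a post-dose event. All analyses are descriptive, so no test result is at stake. Each patient counts once per preferred term, so a Day 0 event adds nothing for a patient who has the same event later. Low glucose before dosing on Days 7 and 14, and hypoglycemia reported during follow-up, stays treatment-emergent under either rule, so correcting the flag will not clear a hypoglycemia row of insulin-related events.

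Two further points have some force. AE listings will carry a phase flag, so Day 0 events can be found by hand. The eCRF is not among the documents and the SAP computes AE duration from dates alone, so completeness of onset times cannot be confirmed.

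These arguments limit the consequence. They do not reconcile the definition with the algorithm, and they leave the overlap with the screening phase untouched.

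**Conclusion.** The inconsistency stands and follows from the text alone. SAP 14.1.1 does not implement the SAP's definition of a treatment-emergent AE, and its screening sentence lets any event on the date of first administration meet both phase conditions. Misclassification against the definition is confined to events on that date before the injection. It inflates TEAE counts in both arms about equally and modestly dilutes the relative comparison with GlucaGen.

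The size is unknown. The figures of about 1 to 11 patients per arm in a hypoglycemia row, and about 0.6 to 10 in the any-TEAE row, rest wholly on assumed rates and serve only to show scale. Confidence is high that the rules conflict, and low on how much the tables would change. The correction is worth making because it is cheap and removes a programming choice from the safety tables.

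**What to change.** Amend SAP 14.1.1 in three respects:

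1. Classify an AE as treatment-emergent when its onset date and time are at or after the time of the first injection.
2. For an AE on the day of first injection, apply the date-only rule only when onset time is missing. This includes onsets imputed to the first-dose date under SAP section 9, which carry no time.
3. Define screening-phase AEs as those with onset before the first administration, so that the two phases are mutually exclusive.

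The definitions section then needs no change. The cost is a few lines of SAP text and a small change to the flagging program. No new data are required: the protocol already asks for onset time, and the post-dose sampling schedule presupposes a recorded injection time. Reporting how many Day 0 AEs lack an onset time would show how far the fallback was used.

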14.1.2 Summary of adverse events

An overview AE summary table will be prepared showing the number and percentage of subjects with at least one event and the total number of events for the following selections:

1. Adverse events during screening
2. treatment-emergent AEs (TEAEs)
3. TEAEs, which are clinical events of interest

4. TEAEs, which are injection site reactions
5. study drug-related TEAEs (Adverse Drug Reactions (ADRs))
6. serious TEAEs (SAEs)
7. study drug-related serious TEAEs (serious ADRs)
8. Deaths

The summary table is based on the number of AE verbatims.

14.1.3 Adverse event tables

In addition, frequency tables will be prepared stratified by MedDRA terms (SOC, PT) showing the following:

1. All TEAEs
2. All clinical events of interest
3. All injection site reactions
4. Study-drug related TEAEs (ADRs)
5. TEAEs by causal relationship to study drug
6. TEAEs by intensity grading
7. Serious TEAEs (SAEs)

The analysis of AEs will include summary tables displaying counts and percentages of subjects experiencing adverse events by system organ class and preferred term. If a subject has more than one AE which codes to the same preferred term, the subject will be counted only once for that preferred term. The total number of events documented per system order class (SOC) and preferred team (PT) will also be displayed.

14.1.4 Vital signs related to clinical events of interest

A descriptive statistics tabulation by treatment group will show systolic and diastolic pressure (mmHg) and pulse rate (bpm) of MedDRA coded clinical events of interest for each SOC and PT. A footnote will indicate that results are based on MedDRA coded number of clinical events and not on number of patients.

14.1.5 Local tolerability

Number/ percentage of patients experiencing any injection site reactions at 0.5 hour and 2 hours post-dose will be tabulated by treatment group for each visit.

14.2 Routine laboratory

14.2.1 General

- High (H)/ Low (L) flags will be presented in laboratory listings, where appropriate. If normal ranges are not available, the flagging cannot be performed.
- All data will be listed in the clinical study report as raw data. For the summaries the most recent value will be used in case several measurements have been performed at one visit.

Tabulations will be prepared for each laboratory parameter by treatment group:

1. Laboratory results with continuous variables will be presented with descriptive statistics for each scheduled time point. They will be marked whether they are below (L), within or above (H) the respective reference range. The numbers in each category (above/below/within reference range) will be counted and percentages presented for each laboratory test result, visit and time point.
2. If laboratory values are categorical, the results (e.g. positive/ negative) will be presented with counts and percentages for each visit and time point available.
3. Presentation of 'change from baseline' values: Change from baseline will be evaluated for all laboratory parameters. The change will be calculated by building the difference between the pre-dose value and each post-dose measurement at each visit. Change from baseline values will be presented with descriptive statistics in case of continuous parameters. In case of categorical parameters shift tables will be presented.

14.2.2 Hematology

Tabulation will follow presentation as suggested in section 14.2.1, items # 1 to #3. No figures will be prepared.

14.2.3 Clinical chemistry

Tabulation will follow presentation as suggested in section 14.2.1, items # 1 to #3. No figures will be prepared.

14.2.4 Coagulation

Coagulation parameters at screening will be tabulated with descriptive statistics by treatment group.

14.2.5 Urinalysis

Tabulation will follow presentation as suggested in section 14.2.1, items # 1 to #3. No figures will be prepared.

14.2.6 Child bearing potential and pregnancy test

Data concerning child bearing potential and results of pregnancy test will be tabulated with counts/ percentages for each visit by treatment group.

14.2.7 Drug screening (urine drug screen)

Data on drug screening will be listed.

14.2.8 Alcohol breath test

Data on alcohol breath test will be listed.

14.3 Physical examination and vital signs

14.3.1 Body measurements (weight, height, BMI) and vital signs (blood pressure, pulse rate, body temperature)

Details of vital signs (systolic and diastolic pressure (mmHg), pulse rate (bps), body temperature (C° Celsius)) will be tabulated by treatment group, visit and time point. Change from baseline for vital sign parameters will be calculated as the difference between the pre-dose value and each post-dose measurement per visit.

Body measurements, which are evaluated at screening only, i.e. weight (kg), height (cm) and BMI (kg/ m²), will be tabulated by treatment group.

Temperature, height and weight will be presented in C° Celsius, cm and kg using the following formulas:

Parameter	Re-calculation formula
Temperature	Temperature [Celsius °C] $= (\text{Temperature [Fahrenheit °F]} - 32) * \frac{5}{9}$
Height	Height (cm) = Height (inches) * 2.54
Weight	Weight (kg) = Weight (lbs.) * 0.4534

